8.3.2 Method of Detecting AEs, SAEs, and pIMDs

Detecting and recording of AE/SAE/pIMDs are detailed in [Appendix 3](#).

The method of recording, evaluating, and assessing causality of AE and SAE and the procedures for completing and transmitting safety reports are provided in [Appendix 3](#).

Care will be taken not to introduce bias when detecting AEs and/or SAEs. Open-ended and non-leading verbal questioning of participants is the preferred method of acquiring information related to an AE/SAE/pIMD.

8.3.3 Follow-up of AEs, SAEs, and pIMDs

After the initial AE/SAE report, the investigator is required to proactively follow each participant at subsequent visits/contacts. All SAEs and pIMDs as defined in Section [10.3.3.1](#) will be followed until resolution, stabilization, the event is otherwise explained, or the participant is lost to follow-up (as defined in [Section 7.3](#)). Further information on follow-up procedures is provided in [Section 10.3.5](#).

8.3.4 Regulatory Reporting Requirements for SAEs and Other Events

Once an investigator (or designee) becomes aware that a study participant has experienced an SAE/pIMD, it must be reported to IQVIA using the required documentation and within the timeframes mentioned in [Table 11](#). This is essential for meeting GSK legal obligations and ethical responsibilities for participant safety and the safety of a study intervention under clinical investigation.

For SAEs/pIMDs, the investigator must always provide an assessment of causality at the time of the initial report, as defined in the [Appendix 3](#).

Local regulatory requirements and sponsor policy for preparation of an investigator safety report of Suspected Unexpected Serious Adverse Reactions (SUSAR) must be followed. These reports will be forwarded to investigators as necessary.

GSK has the legal responsibility to notify local authorities/regulatory agencies about the safety of an investigational study intervention. GSK will comply with country--specific regulatory requirements related to safety reporting to the regulatory authority, IRB/IEC, and investigators.

Refer to [Appendix 3](#) for further details regarding the reporting of SAEs/pIMDs.

An investigator who receives an investigator safety report describing an SAE or other specific safety information (e.g., summary or listing of SAEs) from GSK will review and then file it along with the IB and will notify the IRB/IEC, if appropriate according to local requirements.

Table 11 Timeframes for Submitting SAE and Other Events Reports to IQVIA

Type of Event	Initial Reports		Follow-up of Relevant Information on a Previous Report	
	Timeframe	Documents	Timeframe	Documents
SAEs	24 hours*, ‡‡	Electronic‡ Expedited Adverse Events Report	24 hours*	Electronic‡ Expedited Adverse Events Report
pIMDs	24 hours**, ‡‡	Electronic‡ Expedited Adverse Events Report	24 hours*	Electronic‡ Expedited Adverse Events Report

pIMD=potential immune-mediated disease; SAE=serious adverse events.

* Timeframe allowed after receipt or awareness of the information by the investigator/site staff.

**Timeframe allowed once the investigator determines that the event meets the protocol definition of a pIMD.

‡ Paper Expedited Adverse Events Report may be submitted in the case that the electronic Expedited Adverse Report system is not functioning. The paper form will be dated and signed by the investigator (or designee).

‡‡ The investigator will be required to confirm review of the SAE/pIMD causality by ticking the ‘reviewed’ box in the electronic Expedited Adverse Events Report within 72 hours of submission of the SAE/pIMD.

8.3.5 Treatment of Adverse Events

Any medication, vaccine or products which may explain/cause/be used to treat an SAE/pIMD should be recorded in the Expedited Adverse Event Report of the participant’s eCRF.

8.3.6 Medical Device Deficiencies

Medical devices are being provided for use in this study as the study intervention. To fulfill regulatory reporting obligations worldwide, the investigator is responsible for the detection and documentation of events meeting the definitions of device deficiency that occur during the study with such devices.

The definition of a medical device deficiency can be found in [Appendix 3](#).

NOTE: Device deficiencies that lead to an AE/SAE will be reported as an AE/SAE following the processes outlined in [Appendix 3](#) of the protocol.

8.3.6.1 Time Period for Detecting Medical Device Deficiencies

Medical device deficiencies will be detected, documented, and reported during all periods of the study in which the medical device is used.

If the investigator learns of any device deficiency at any time after a participant has been discharged from the study, and such a device deficiency might have led to an SAE if

appropriate action had not been taken, intervention had not occurred, or circumstances had been less fortunate, the investigator will promptly notify GSK.

The method of documenting medical device deficiencies is provided in [Appendix 3](#).

8.3.6.2 Follow-up of Medical Device Deficiencies

Follow-up applies to all participants, including those who discontinue study intervention.

The investigator is responsible for ensuring that follow-up includes any supplemental investigations as indicated to elucidate the nature and/or causality of the deficiency.

New or updated information will be recorded on the originally completed form with all changes signed and dated by the investigator.

8.3.6.3 Prompt Reporting of Device Deficiencies to the Sponsor

Device deficiencies will be reported to the Sponsor or designee within 24 hours after the investigator determines that the event meets the protocol definition of a medical device deficiency.

The medical device deficiency report form will be sent to GSK as described in [Appendix 3](#).

GSK will be the contact for the receipt of device deficiency reports.

8.3.6.4 Regulatory Reporting Requirements for Device Deficiencies

The investigator will promptly report all device deficiencies occurring with any medical device provided for use in the study in order for the Sponsor to fulfill the legal responsibility to notify appropriate regulatory authorities and other entities about certain safety information relating to medical devices being used in clinical studies.

The investigator, or responsible person according to local requirements (e.g., the head of the medical institution), will comply with the applicable local regulatory requirements relating to the reporting of device deficiencies to the IRB/IEC.

8.4 Participant Card

The investigator (or designee) must provide the participant with a “participant card” containing information about the clinical study. The participant must be instructed to always keep the participant card in his/her/their possession for the duration of the study. In an emergency, this card serves to inform the responsible attending physician/caregiver/family member that the participant is in a clinical study and that relevant information may be obtained by contacting the investigator or his/her backup.

8.5 Pharmacokinetics

Pharmacokinetic parameters are not evaluated in this study.

8.6 Pharmacodynamics

Pharmacodynamic parameters are not evaluated in this study.

8.7 Genetics

Genetics are not evaluated in this study.

8.8 Biomarkers

Biomarkers are not evaluated in this study.

8.9 Immunogenicity Assessments

Immunogenicity is described in [Section 8.1](#).

8.10 Health Outcomes

Not applicable for this study.

8.11 Health Economics

Health economics parameters are not evaluated in this study.

9.0 STATISTICAL CONSIDERATIONS

9.1 Statistical Hypotheses

Statistical hypotheses are associated to the confirmatory primary non-inferiority (NI) objectives, which will be tested to control overall Type 1 error. Global Type I error is controlled at 2.5% (1-sided). The NI margins associated to each objective are provided in Table 12.

Table 12 Study Objectives and Null Hypothesis

Objectives	Null hypothesis
Primary	

 To demonstrate the non-inferiority of PCV20 when co-administered with the RSVPreF3 OA investigational vaccine compared to PCV20 administered alone. 	
 True Group GMT ratio between the Control group (PCV20 vaccine) divided by Co-ad group (RSVPreF3 OA investigational vaccine when co-administered with the PCV20 vaccine) in OP Ab titer for each PCV serotypes one month after the PCV20 is above 2.

 To demonstrate the non-inferiority of RSVPreF3 OA investigational vaccine in terms of RSV-A neutralization antibodies when co-administered with PCV20 compared to RSVPreF3 OA investigational vaccine administered alone. 	
 True GMT ratio between Control group (RSVPreF3 OA investigational vaccine) divided by Co-ad group (RSVPreF3 OA investigational vaccine when co-administered with the PCV20 vaccine) in RSV-A neutralizing antibody (Ab) titers one month after the RSVPreF3 OA investigational vaccine dose is above 1.5.

 To demonstrate the non-inferiority of RSVPreF3 OA investigational vaccine in terms of RSV-B neutralization antibodies when co-administered with PCV20 compared to RSVPreF3 OA investigational vaccine administered alone. 	
 True GMT ratio between Control group (RSVPreF3 OA investigational vaccine) divided by Co-ad group (RSVPreF3 OA investigational vaccine when co-administered with the PCV20 vaccine) in RSV-B neutralizing Ab titers one month after the RSVPreF3 OA investigational vaccine dose is above 1.5.

Abbreviations: Ab=Antibody; GMT=Geometric mean titer; OP=Opsonophagocytic; PCV20=20-valent pneumococcal vaccine; RSVPreF3 OA= respiratory syncytial virus PreFusion protein 3 older adult investigational vaccine.

Statistical testing of each endpoint will be performed sequentially to control the Global Type I error below 2.5% (1-sided). The testing sequence is detailed in [Section 9.3.1.1](#).

9.2 Populations for Analysis

Populations for analyses in this study are defined in Table 13.

Table 13 Analysis Sets

Analysis Set	Description
Screened set	All participants who were screened for eligibility.
Enrolled set	Participants who were randomized or received study intervention or have undergone an invasive procedure.
ES	All participants who received a study intervention. Analysis per group is based on the study intervention administered.
PPS	All eligible participants: 
 • Who received all study interventions as per protocol • Had immunogenicity results pre- and post-dose • Complied with blood draw intervals (contribution of participants to PPS at specific timepoint will be defined by timepoint) • Without intercurrent medical conditions that may interfere with immunogenicity • Without prohibited concomitant medication/vaccination

Abbreviations: ES=Exposed set; PPS=Per Protocol set.

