7.1 Discontinuation of Study Intervention

Discontinuation of study intervention refers to any participant who has not received all planned doses of study intervention. A participant who discontinued study intervention may continue other study procedures (e.g., safety or immunogenicity), planned in the study protocol at the discretion of the investigator.

The primary reason for premature discontinuation of the study intervention will be documented on the eCRF as follows:

- Adverse event requiring expedited reporting to IQVIA
- Unsolicited non-serious adverse event
- Solicited adverse event
- Not willing to be vaccinated
- Other (specify)

If a participant who does not meet enrollment criteria is inadvertently enrolled, that participant must be discontinued from study intervention and IQVIA must be contacted. An exception may be granted in rare circumstances for which there is a compelling safety reason to allow the participant to continue. In these rare cases, the investigator must obtain documented approval from GSK, or designee, to allow the participant to continue in the study.

Participants who discontinue study intervention will not be replaced.

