7.1.1 Contraindications to Subsequent Study Intervention Administration

The eligibility for subsequent study intervention administration in the control group must be confirmed before administering any additional dose.

Participants who meet any of the criteria listed below or criteria listed in [sections 5.2.1](#) and [5.2.2](#) should not receive additional doses of study intervention. Such participants should be encouraged to continue other study procedures, at the investigator's discretion ([10.3](#)). All relevant criteria for discontinuation of study intervention administration must be recorded in the eCRF.

- Participants who experience any SAE judged to be possibly or probably related to the first study intervention (PCV20 vaccine) and that, in the opinion of the investigator, may pose

additional risk to the participant if he/she receives the second study intervention (RSV investigational vaccine).

- Participants who develop any new condition which, in the opinion of the investigator, may pose additional risk to the participant if he/she continues to participate in the study.
- Anaphylaxis following the administration of study intervention(s) from Visit 1 onwards.
- Any condition that in the judgment of the investigator would make intramuscular injection unsafe.

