9.2.1 Criteria for Elimination

If the participant meets one of the criteria mentioned below or any listed in the [Section 7.1.1](#), (contraindication to subsequent vaccination) or [Section 5.2.1](#) (medical conditions) or [Section 5.2.2](#) (prior and concomitant therapy), he/she may be eliminated from per protocol analysis.

In case of unplanned administration of any medication mentioned in [Section 5.2.2](#) during the study, this will be considered as a protocol deviation and the participant may be eliminated from the Per Protocol set (PPS).

Participants may be eliminated from the PPS for immunogenicity if, during the study, they incur a condition that has the capability of altering their immune response (intercurrent medical condition) or are confirmed to have an alteration of their initial immune status. Refer to [Glossary of Terms](#) for the definition of intercurrent medical conditions.

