2.4. Estimands

The primary and secondary estimands to support regulatory decisions are described in the following table:

	Study Intervention	Population	Variable (or endpoint)	Intercurrent events (ICEs)		Population level summary
				Description	Handling strategy	
Primary	RSVPreF3 OA and PCV20 co-administered (Co-Ad) or received separately (Control)	Adults aged \geq 60 years of age (YOA)	Geometric Mean Titers (GMTs) for opsonophagocytic (OP) antibodies (Ab) titers for each of the pneumococcal vaccine serotypes (STs)	
 1. Permanently discontinued from study due to any reasons prior to Visit 2 blood sampling 2. Study intervention not administered per protocol 3. Prohibited medication or intercurrent medical condition prior to Visit 2 blood sampling 4. Vaccine or blood sample taken out of window 5. No pre/ post-vaccine immunogenicity result available 	
 1. Missing data won't be imputed. Summaries will present the actual data. 2. Participant excluded from the immunogenicity analysis. 3. Participant excluded from the immunogenicity analysis. 4. Participant excluded from the immunogenicity analysis. 5. Participant excluded from the immunogenicity analysis. 	Between group 2-sided 95% CI for the group GMT ratio in terms of OP antibody titers for each of the pneumococcal vaccine STs for PCV20 vaccine administered alone (Control) over PCV20 vaccine co-administered with RSVPreF3 investigational vaccine (Co-Ad group) at 1 month after the PCV20 vaccine (at Visit 2 for both groups).
Primary	RSVPreF3 OA and PCV20 co-administered (Co-Ad) or received separately (Control)	Adults aged \geq 60 YOA	GMTs for RSV-A neutralizing Ab titers	
 1. Permanently discontinued from study due to any reasons within 30 days of vaccine administration (Visit 2 for Co-Ad group; Visit 3 for Control group) 2. Study intervention not administered per protocol 	
 1. Missing data won't be imputed. Summaries will present the actual data. 2. Participant excluded from the immunogenicity analysis. 3. Participant excluded from the immunogenicity analysis. 	Between group 2-sided 95% CI for the group GMT ratio in terms of RSV-A neutralizing Ab titers for RSVPreF3 investigational vaccine administered alone (Control) over RSVPreF3 investigational vaccine co-

CCI [REDACTED]

PPD [REDACTED]

CCI [REDACTED]

[REDACTED]

[REDACTED]

[REDACTED]

[REDACTED]

[REDACTED]

[REDACTED]

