5.5. Per Protocol Set [PPS]

RSV PPS:

All eligible participants in the ES:

- who received RSV vaccine as per protocol in the control group and received both study interventions in the Co-Ad group
- who had immunogenicity results pre- and post-dose for RSV neutralizing titers
- who complied with blood draw interval for RSV samples
- without intercurrent medical conditions* that may interfere with immunogenicity and without prohibited concomitant medication / vaccination up to blood sample post RSV vaccination for control group and Co-Ad group,
- who do not meet any of the criteria for elimination up to blood sample post RSV vaccination for control group and Co-Ad group (i.e., control group participants need to meet all above criteria at Visits 2 and 3; Co-Ad group participants need to meet all above criteria at Visits 1 and 2).

PCV PPS:

All eligible participants in the ES:

- who received PCV vaccine as per protocol in the control group and received both study interventions in the Co-Ad group
- who had immunogenicity results pre- and post-dose for opsonophagocytic antibodies (OP Ab) titers
- who complied with blood draw interval for PCV20 samples
- without intercurrent medical conditions that may interfere with immunogenicity and without prohibited concomitant medication / vaccination* up to blood sample post PCV20 vaccination for control group and Co-Ad group, and
- who do not meet any of the criteria for elimination up to blood sample post RSV vaccination for control group and Co-Ad group (i.e., control group and Co-Ad group participants need to meet all above criteria at Visits 1 and 2)

*Intercurrent medical conditions that may lead to elimination from the PPS are defined as confirmed immunodeficiency condition, use of prohibited medication, or development of RSV or pneumococcal disease in the interval between study intervention administration and the collection of blood specimen for immunogenicity (i.e., Day 31 for Co-Ad group for PCV20 intervention; Day 31 for Co-Ad group and Day 61 for Control group for RSVPreF3 OA intervention).

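### The confirmatory PCV20 per-protocol set is defined inconsistently: some rules drop a Control participant for an RSV dose missed, or an event occurring, after the Day 31 endpoint sample, and others keep that participant

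*Protocol*

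**What the plan says.** **Timing.** Control receives PCV20 at Visit 1 and RSVPreF3 OA at Visit 2. The Visit 2 blood sample is both the post-PCV20 sample and the RSV baseline (Protocol 1.3, Table 2 footnotes; Table 8), so it precedes the RSV dose. Co-Ad receives both vaccines at Visit 1.

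**Protocol 9.2, Table 13.** There is one PPS, with the dosing criterion "Who received all study interventions as per protocol". A note that "contribution of participants to PPS at specific timepoint will be defined by timepoint" is attached to the blood-draw criterion, not to the dosing criterion. Protocol 9.3.1 bases the confirmatory analyses on the PPS.

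**Protocol 9.2.1.** A participant who meets a criterion in 7.1.1 ("contraindication to subsequent vaccination"), 5.2.1 or 5.2.2 is one of whom it is said that "he/she may be eliminated from per protocol analysis".

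**SAP 2.4, PCV20 row.** Event 2 is "Study intervention not administered per protocol", handled by exclusion. Events 1 and 3 in the same row stop at the Visit 2 sample; event 2 does not. Event 4, on vaccine or sample out of window, has no such limit either.

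**SAP 5.5, PCV PPS.** The dosing bullet requires participants "who received PCV vaccine as per protocol in the control group and received both study interventions in the Co-Ad group". The last bullet applies the elimination criteria until the sample that follows RSV vaccination, which is Day 61 in Control, while its bracket refers to Visits 1 and 2.

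**SAP 3.3** declares no change from the protocol's analyses.

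**The concern.** Whether a Control participant receives the RSV dose, or receives it on time, cannot alter a titer in blood already drawn. A rule that removes the participant from the PCV20 comparison on that ground is a post-randomisation exclusion based on something that happens after the endpoint. It has no counterpart in Co-Ad, where both doses precede the Day 31 sample by a month and the post-RSV sample is that same Day 31 sample.

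The case is foreseeable. Protocol 7.1 lists "Not willing to be vaccinated" as a reason for stopping the intervention and lets such participants continue other procedures. Protocol 5.6 does not list blood sampling among the steps to repeat when the Control Visit 2 dose is delayed. Protocol 8.0 allows 30 extra days for that dose in exceptional situations and leaves the effect on the PPS to case-by-case decision.

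Two things are at stake: a confirmatory set with a single definition in an open-label trial, and comparability of the arms for all 20 serotypes, each of which must pass.

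**Working it through.** **1. One participant under each rule.** Take a Control participant who received PCV20 correctly, gave an in-window Day 31 sample, and then did not receive the RSV dose.

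| Rule | PCV20 analysis |
|---|---|
| Protocol Table 13, read literally | Excluded |
| SAP 2.4 PCV20 row, event 2, read literally | Excluded |
| Protocol 9.2.1 | Eliminable only if a listed condition applies; a refusal is not listed |
| SAP 5.5 PCV PPS, dosing bullet | Kept |
| SAP 5.5 PCV PPS, last bullet | Depends on whether the window closes at Day 61 or Visit 2 |

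**2. The plan's own power.** Inputs from Protocol 9.5 and SAP 2.5: 490 evaluable per arm, one-sided 2.5%, true ratio 1.05, margins 2 and 1.5, log10 SDs of 0.572 to 1.096 for the serotypes and 0.45 for RSV-A and RSV-B. Each type II error comes from a noncentral t-test with noncentrality log10(margin/1.05) / (SD × √(2/490)), and the errors are summed.

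- Serotype 23F: log10(2/1.05) = 0.280; 1.096 × √(2/490) = 0.070; type II error 2.10% (stated 2.10%).
- Sum over 20 serotypes: 6.10% (stated ~6.2%).
- RSV-A and RSV-B: 0.03% each (stated 0.04%).
- Study power: 100 − 6.10 − 0.06 = 93.8% (stated ~93.7%).

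The plan's figure is reproduced.

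**3. Effect of the exclusion.** The documents give neither a rate of missed RSV doses nor a titer difference, so both are assumptions. If a fraction f of Control is removed and their mean log10 titer is d below that of the rest, the Control mean rises by f × d and the Control/Co-Ad ratio is multiplied by 10^(f × d). Take f = 1–5% (5 to 27 of 545) and d = 0.2–0.4, shift only the PCV20 ratios, and keep 490 per arm.

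| f, d | f × d | Multiplier | Ratio from 1.05 | Study power |
|---|---|---|---|---|
| None | 0 | 1 | 1.05 | 93.8% |
| 1%, 0.2 | 0.002 | 1.005 | 1.055 | 93.3% |
| 5%, 0.4 | 0.020 | 1.047 | 1.10 | 86.4% |

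The sign can reverse. If 5% are removed and have twice the GMT of the rest, the multiplier is 10^(−0.05 × log10 2) = 0.966, which favours non-inferiority.

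**4. Loss without bias.** Removing 27 Control participants (463 against 490) gives study power of 92.7%.

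**The case against.** The strongest reply is that SAP 5.5 is the operative rule. SAP 5.1 assigns participants by the SAP's definitions, the protocol describes its statistical section as a summary, and the SAP 5.5 dosing bullet is already the right one. Event 2 in SAP 2.4 can be read in line with it, since the study-intervention text naming both vaccines is the same in every row. A deviation management plan, a data review meeting and sponsor authorisation precede database lock, and the testing laboratory is blinded. Much of this stands, and it shows the likely intention. But SAP 2.4 and 5.5 are parts of the same document, event 2 lacks the limit given to events 1 and 3, and the last bullet of the PCV PPS contradicts its own bracket. A review before lock needs one rule to apply.

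A reader might infer that Protocol 9.2.1 itself removes these participants, and that health-related elimination reaches Control alone. The text does not support this. Section 9.2.1 is permissive and does not list a missed dose. It is true of the Control second dose that "The eligibility for subsequent study intervention administration in the control group must be confirmed before administering any additional dose", but several 7.1.1 criteria are not worded for one arm, and 5.2.1, 5.2.2 and the intercurrent-condition rules apply to both. Only exclusion for a dose missed, or an event occurring, after the Day 31 sample is specific to Control.

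SAP 15 adds an analysis on the Exposed Set when 5% or more of vaccinated participants with results are excluded in a group. This is a partial safeguard: 27 of 545 is 4.95%, just short of the trigger unless there are other exclusions, and the added analysis only complements the PPS result.

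**Conclusion.** The inconsistency holds. Protocol Table 13 and SAP 2.4, read literally, exclude a participant whom the SAP 5.5 dosing bullet keeps; SAP 5.5 gives two end points for PCV elimination; and SAP 3.3 does not declare the split of the PPS. The resulting exclusion is confined to Control and unrelated to the Day 31 titer.

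Its effect cannot be fixed from the documents. A reader might infer a known bias against non-inferiority, or a fall to the ~85% power that SAP 2.5 gives for a ratio of 1.1. Neither follows. The direction depends on who misses the dose, and refusals unrelated to response cause no bias. The ~85% figure (85.7% on recalculation) also moves RSV-A and RSV-B to 1.1, which this mechanism does not touch; moving PCV20 alone gives 86.4%, and only when 5% are lost, all averaging 0.4 log10 lower in every serotype. At the low end the change is half a point. The shift is also unadjusted, and the ANCOVA on age and pre-dose titer could absorb part of it. The point should be corrected because the confirmatory set ought to have one definition, not because a large loss of power has been shown.

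**What to change.** - **(a) Protocol Table 13:** define the PPS by vaccine, using the SAP 5.5 dosing rule (PCV20 in Control, both vaccines in Co-Ad, for the PCV20 comparison).
- **(b) SAP 2.4, PCV20 row:** limit events 2 and 4 to the doses and samples due up to the Visit 2 sample.
- **(c) SAP 5.5, last PCV PPS bullet:** end the elimination window at the post-PCV20 sample (Visit 2) in both arms.
- **(d) Protocol 9.2.1 and SAP 5.5:** state that non-receipt or out-of-window receipt of the RSV dose in Control does not by itself eliminate from the PCV PPS. Immune-altering conditions and prohibited products before the Visit 2 sample should still do so in both arms. A blanket exemption for every 7.1.1 contraindication would be too wide, because 7.1.1 takes in 5.2.1 and 5.2.2 and would keep participants who became immunosuppressed before Day 31.
- **(e) SAP 3.3:** list the vaccine-specific PPS as a change from the protocol.

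The cost is SAP wording and a protocol clarification. No new data are needed, since the Day 31 sample is already planned and tested for all participants.
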